## 1. PROTOCOL SUMMARY

### 1.1. Protocol Synopsis

**Protocol Title:** A Multicenter, Randomized, Double-Blind, Placebo-Controlled, Parallel-Group Study Comparing the Efficacy, Safety, and Tolerability of Subcutaneous Administration of Fremanezumab Versus Placebo for the Preventive Treatment of Chronic Migraine in Pediatric Patients 6 to 17 Years of Age

**Brief Title:** Randomized, Double-Blind, Placebo-Controlled Trial of Fremanezumab in Participants (6 to 17 Years) with Chronic Migraine. A Trial to Test if Fremanezumab is Effective in Preventing Chronic Migraine in Patients 6 to 17 Years of Age.

**Regulatory Agency Identifier Number(s):** IND number: 106,533; NDA number: not applicable; BLA number: 761089; EudraCT number: 2019-002053-33; EU CT number: not applicable

**Pediatric Investigation Plan Number:** P/0378/2023

**Rationale:** Migraine is a prevalent condition characterized by attacks of headache and associated symptoms (such as nausea, photophobia, or phonophobia). Among populations of children of all ages, migraine prevalence ranges from 8% to 11%. There is an unmet medical need for a safe and effective prophylactic treatment for episodic migraine and chronic migraine (CM) in the pediatric population. Given the progression of the disease and the knowledge gained from the adult population, it is reasonable and important to evaluate fremanezumab in the pediatric population.

**Name of IMP:** Fremanezumab

**Intervention Type:** Drug (including placebo)

**Primary and Secondary Objectives, Endpoints:**

Objectives	Endpoints
The primary objective of the trial is to evaluate the efficacy of test investigational medicinal product (IMP) as compared to placebo IMP for the preventive treatment of chronic migraine (CM).	The primary efficacy endpoint is the mean change from baseline (28-day baseline period) in the monthly average number of migraine days during the 12-week period after the first dose of IMP.
A secondary objective is to evaluate the safety and tolerability of test IMP in the preventive treatment of CM.	The safety and tolerability endpoints are as follows: 
 
occurrence of adverse events throughout the trial, including local injection site reaction/pain
 
abnormal standard 12-lead electrocardiogram (ECG) findings
 
changes from baseline in vital signs (systolic and diastolic blood pressure, pulse, temperature, and respiratory rate), height, and weight measurements
 
changes from baseline in clinical laboratory (serum chemistry, hematology, coagulation, and urinalysis) test results
 
abnormal physical examination findings
 

Objectives	Endpoints

A secondary objective of the trial is to further demonstrate the efficacy of test IMP as compared to placebo IMP for the preventive treatment of CM.
	
 
suicidal ideation and behavior as suggested by the Columbia-Suicide Severity Rating Scale (C-SSRS)
 
 
The secondary efficacy endpoints are as follows:
 
 
mean change from baseline (28-day baseline period) in monthly average number of headache days of at least moderate severity during the 12-week period after the first dose of IMP
 
proportion of participants reaching at least 50% reduction in the monthly average number of migraine days during the 12-week period after the first dose of IMP
 
mean change from baseline (28-day baseline period) in the monthly average number of days of use of any acute headache medications during the 12-week period after the first dose of IMP
 
mean change from baseline (day 1) in migraine-related disability score, as measured by the Pediatric Migraine Disability Assessment (PedMIDAS) questionnaire, at 12 weeks after administration of the first dose of IMP
 
mean change from baseline (day 1) in quality of life, as measured by the Pediatric Quality of Life Inventory (PedsQL), at 12 weeks after administration of the first dose of IMP
 

A secondary objective of the trial is to evaluate the immunogenicity of test IMP and the impact of antidrug antibodies (ADAs) on clinical outcomes in participants exposed to test IMP.
	
 
proportion of participants developing ADAs throughout the trial. The impact of ADAs on safety and efficacy will be analyzed if the number of ADA-positive participants allows.
 

Exploratory objectives and endpoints will be assessed as well.

**Overall Design:** This is a 4-month, multicenter, randomized, double-blind, placebo-controlled, parallel-group trial to evaluate the efficacy, safety, and tolerability of 2 different doses (dependent on participants' body weight) of subcutaneous (sc) test investigational medicinal product (IMP) and placebo IMP. Enrollment will include male and female participants (6 to 17 years of age, inclusive). The dose of test IMP will be determined by the participant's weight at randomization.

**Number of Participants:** A planned total of approximately 278 CM participants will be randomized. The number of evaluable participants is planned to be approximately 266 (133 evaluable participants completing the trial per treatment group).

**Trial Arms and Duration:** Participants will be randomly assigned in a 1:1 ratio between test IMP and placebo IMP treatment groups. The total duration of the trial is planned to be 75 months (from quarter [Q]2 2020 to Q3 2026).

[figure not shown]
**Data Monitoring/Other Committee:** Not applicable.

**Ethical Considerations:** Based on the current safety profile and the demonstrated efficacy of the sc test IMP dosage form as observed in adults, the overall risk and benefit assessment for this trial is favorable.

[figure not shown]
## 1.2. Trial Schema

Figure 1: Overall Trial Schematic Diagram

Participants weighing  $\geq 45.0$  kg at randomization:

Participants weighing  $<45.0$  kg at randomization:

PBO=placebo; SC=subcutaneous; V=visit.

### 1.3. Schedule of Activities

Trial procedures and assessments with their time points are presented in [Table 1](#). Detailed descriptions of each method of procedures and assessments are provided in Section [8](#) (Trial Assessments and Procedures) and Section [13.9](#).

**Table 1: Trial Procedures and Assessments**

Trial period	Pretreatment period (incl. screening visit and baseline period)						Double-blind treatment period					
	V1 a	V2	V3	V4	V5 b	Month -1	Month 0	Month 1	Month 2	Month 3	EOT or early withdrawal	Day 85 d (±3 days)
Visit number												
Month number												
Procedures and assessments c	Screening Days -28 to -1	Randomization Dose 1 Day 1 d (+3 days)	Dose 2 Day 29 d (±3 days)	Dose 3 Day 57 d (±3 days)	EOT or early withdrawal Day 85 d (±3 days)							
Informed consent and assent e	X											
Inform participants of trial restrictions and compliance requirements f	X											
Medical and psychiatric history f	X											
Headache history f	X											
Lifetime prior medication and treatment history f	X											
Record demographic characteristics f	X											
Inclusion and exclusion criteria	X		X g									
Physical examination, including weight and height h	X	X									X	
Puberty assessment i,f		X									X	
Randomization j		X										
TriPLICATE 12-lead ECG k	X	X	X	X	X							

Trial period	Pretreatment period (incl. screening visit and baseline period)	Double-blind treatment period			
		V1 a	V2	V3	V4
Visit number	Month -1	Month 0	Month 1	Month 2	Month 3
Procedures and assessments c	Screening Days -28 to -1	Randomization Dose 1 Day 1 d (+3 days)	Dose 2 Day 29 d (±3 days)	Dose 3 Day 57 d (±3 days)	EOT or early withdrawal Day 85 d (±3 days)
Vital signs measurement l	X	X	X	X	X
Adverse events m,f	X	X	X	X	X
Concomitant medication inquiry f	X	X	X	X	X
Clinical laboratory tests c,n	X		X		X
Pregnancy test o	X	X	X	X	X
Electronic headache diary device dispensation p	X				
Review electronic headache diary entries p,f		X	X	X	X
Electronic headache diary device return p					X
Blood samples for plasma drug concentration c		X	X		X
Blood samples for serum ADA assessment c		X	X		X
C-SSRS q,f	X	X	X	X	X
PedMIDAS f		X			X
PedsQL f		X	X	X	X
████████████████████ f					X
Administration of IMP r		X	X	X	

Trial period	Pretreatment period (incl. screening visit and baseline period)	Double-blind treatment period			
		V1 a	V2	V3	V4
Visit number	Month -1	Month 0	Month 1	Month 2	Month 3
Procedures and assessments c	Screening Days -28 to -1	Randomization Dose 1 Day 1 d (+3 days)	Dose 2 Day 29 d (±3 days)	Dose 3 Day 57 d (±3 days)	EOT or early withdrawal Day 85 d (±3 days)
Injection site assessment e		X	X	X	

a Participants will complete the screening visit no more than 28 (+3) days before the randomization visit (visit 2 [day 1]).

b After completing EOT assessments/procedures, all eligible participants will be offered enrollment in the long-term safety and tolerability trial (Trial TV48125-CNS-30084).

c Electrocardiograms will be performed, weight will be recorded (visit 2 only), urine pregnancy tests will be performed at all visits prior to dosing, and blood samples will be collected before IMP administration. Assessment of injection site reactions will be performed after administration of each dose of IMP, before the participant leaves the investigational site. All other trial procedures can be performed at any time during the visit.

d The date of the next visit will be calculated based on the actual date of the last administration of IMP.

e Must be performed prior to any trial procedure.

f [REDACTED]

g Eligibility criteria will be confirmed prior to randomization.

h Physical examination, including height and weight, will be performed at screening, randomization, and EOT. Body mass index will be calculated at screening and randomization.

i Puberty status (Tanner staging scale, see Section 8.3.1) will be assessed at randomization (visit 2) and EOT either by participants' self-report or by physical examination according to the Tanner staging card provided.

j Participants will be randomized to receive placebo IMP or 1 of 2 test IMP doses (based on body weight).

k Twelve-lead ECGs will be performed in triplicate at any time during the visit, prior to IMP administration.

l The method for measuring temperature in an individual participant must be the same at each timepoint.

m Inquiries about adverse events will be made before and after IMP administration.

n Serum chemistry, hematology, coagulation, and urinalysis.

o Females who are postmenarchal or ≥12 years of age only. Serum β-HCG tests will be performed at screening (visit 1) and visit 5; urine β-HCG tests will be performed at all visits. Inquire and record start/stop date of menstrual period at each visit.

p Eligible participants will be given an electronic headache diary device and they or a parent/caregiver will be trained in its use and compliance requirements on the day of screening. Participants or parents/caregivers will complete electronic headache diary entries about the previous day daily beginning on day -27 through the EOT/early withdrawal visit. If the participant is unable to complete the diary themselves, then a parent/caregiver will complete the diary for them.

q The C-SSRS will be completed by a qualified rater trained to administer the scale at the investigational center based on discussion with the participant/caregiver at the time points described. Any participant who demonstrates suicidal ideation and/or any suicidal behavior at any point during the trial should be withdrawn from the trial and discontinued from trial treatment. In addition, if a patient endorses suicidal ideation or behavior at any point during the trial (including during screening), the Investigator must explain to the participant/caregiver the need for follow-up with a mental health professional and make any necessary referrals.

r The location of the sc injection should be recorded at each administration visit.

$\beta$ -HCG=beta-human chorionic gonadotropin; ADA=antidrug antibody; C-SSRS=Columbia-Suicide Severity Rating Scale; ECG=electrocardiogram;

EOT=end-of-treatment; PedMIDAS=Pediatric Migraine Disability Assessment; PedsQL=Pediatric Quality of Life Inventory; [REDACTED]

[REDACTED]; sc=subcutaneous; V=visit.

## 2. INTRODUCTION

Fremanezumab is a humanized immunoglobulin G2 (IgG2)  $\Delta$ a/kappa monoclonal antibody (mAb) derived from a murine precursor. In September 2018, fremanezumab was approved in the United States of America (US) for the preventive treatment of migraine in adults and marketed under the trade name AJOVY®. Fremanezumab has also been approved in the European Union (EU) and a number of countries worldwide. Fremanezumab is a potent, selective calcitonin gene-related peptide (CGRP) binder and blocks both CGRP isoforms ( $\alpha$ - and  $\beta$ -CGRP) from binding to the CGRP receptor. While the precise mechanism of action by which fremanezumab prevents migraine is unknown, it is believed that blocking CGRP prevents activation of the trigeminal system. Fremanezumab is highly specific for CGRP and does not bind to closely related family members (eg, amylin, calcitonin, intermedin, and adrenomedullin). Two mutations were introduced into the constant region of the fremanezumab heavy chain to limit antibody effector functions. This loss of function prevents fremanezumab from stimulating antibody-dependent cell-mediated cytotoxicity and triggering complement-mediated lysis; these activities can lead to unwanted consequences, such as cell lysis, opsonization, and cytokine release and inflammation (Armour et al 1999, Zeller et al 2008).

The safety and tolerability of fremanezumab (intravenous [iv] doses of 0.2 to 2000 mg and subcutaneous [sc] doses of 225 to 900 mg) as well as the pharmacokinetic profile of 225 to 900 mg sc and iv have been well characterized in the Phase 1 development program in adults.

Furthermore, the safety and effectiveness of fremanezumab have been demonstrated in 2 Phase 2b trials and 3 Phase 3 trials in adult participants with migraine. The 2 Phase 2b trials were a randomized, double-blind, placebo-controlled Phase 2b trial of 2 sc dosing regimens of fremanezumab (monthly fremanezumab at 900 mg or fremanezumab at 675 mg followed by monthly fremanezumab at 225 mg) in participants with chronic migraine (CM) and a randomized, double-blind, placebo-controlled Phase 2b trial of 2 sc dosing regimens of fremanezumab (monthly fremanezumab at 675 or 225 mg) in participants with episodic migraine (EM).

Two completed, randomized, double-blind, placebo-controlled Phase 3 trials (Trials TV48125-CNS-30049 in CM and TV48125-CNS-30050 in EM and 1 completed, randomized, double-blind Phase 3 long-term safety trial (Trial TV48125-CNS-30051 in migraine [EM and CM]) were conducted to further evaluate the efficacy, safety, and tolerability of various dose regimens of fremanezumab in the preventive treatment of migraine. Additional trials within the migraine development program of fremanezumab include the completed Phase 3b trial (Trial TV48125-CNS-30068) in participants from the EU and US to evaluate the safety and efficacy of fremanezumab in migraine participants who have failed multiple preventive medications, 2 ongoing Phase 2b/3 trials in Japanese and Korean EM and CM participants (Trials 406-102-00002 and 406-102-00001, respectively), and 1 ongoing long-term safety trial (Trial 406-102-00003) in CM and EM to evaluate the safety and efficacy of fremanezumab. One Phase 4 trial (Trial TV48125-MH-40142) was conducted to evaluate the efficacy and safety of fremanezumab in adult participants with migraine and comorbid major depressive disorder.

The pediatric migraine development program includes a completed Phase 1, single-dose, open-label trial with administration of single sc doses of 75 mg in pediatric participants with migraine 6 to 11 years of age, inclusive (Trial TV48125-CNS-10141).

Fremanezumab is further studied for the preventive treatment of persistent posttraumatic headache (PPTH) in 1 Phase 2 trial (Trial TV48125-CNS-20024) that is comparing the efficacy and safety of the sc dose regimen of fremanezumab versus placebo in participants with PPTH. Fremanezumab was being studied for the preventive treatment of cluster headache (CH) in 3 Phase 3 trials: Trial TV48125-CNS-30056 in participants with episodic CH, Trial TV48125-CNS-30057 in participants with chronic CH, and a long-term safety Trial TV48125-CNS-30058 in CH. All 3 trials were terminated by Teva because a prespecified futility analysis showed that the primary endpoint of mean change from baseline in the monthly average number of CH attacks during the 12-week treatment period was unlikely to be met.

Migraine is a prevalent condition characterized by attacks of headache and associated symptoms (such as nausea, photophobia, or phonophobia). Among populations of children of all ages, migraine prevalence ranges from 8% to 11% ([Abu-Arefeh and Russell 1994](#), [Abu-Arefeh et al 2010](#), [Laurell et all 2004](#), [Ozge et al 2013](#), [Stovner and Andree 2010](#)). The prevalence of migraine is substantially lower among children younger than 7 years, ranging from 1% to 3% ([Lewis 2009](#)). The prevalence of migraine in children younger than 12 years is less than one-third of the prevalence among adolescents ([Fendrich et al 2007](#), [Ozge et al 2013](#), [Stovner and Andree 2010](#), [Unalp et al 2007](#)). Therefore, the prevalence of migraine increases throughout childhood, with estimates for adolescents comparable to the 12% to 15% prevalence estimates cited for adult populations ([Buse et al 2013](#), [Burch et al 2015](#), [Stovner and Andree 2010](#), [Victor et al 2010](#)).

Migraine has been classified by headache frequency in the International Classification of Headache Disorders, 3rd revision (ICHD-3) and is described as EM, which is defined as headaches occurring on less than 15 days per month, and CM, which is defined as headaches on at least 15 days per month for at least 3 months, with the features of migraine on at least 8 days per month ([Headache Classification Committee of the IHS 2013](#), [Lipton and Silberstein 2015](#)).

Treatment options for migraine include non-pharmacological biobehavioral strategies and pharmacological strategies. Topiramate is the only migraine preventive medication approved for pediatric populations, but it is not approved in all regions of the EU and is limited to adolescents ages 12 through 17. Non-pharmacological strategies for adults and children with migraine include sleep hygiene, exercise, dietary modifications, biofeedback, and stress management ([O'Brien et al 2012](#), [Silberstein 2000](#)). Pharmacologic agents used for the treatment of migraine can be classified as acute (ie, to alleviate the acute migraine attack) or prophylactic (ie, preventing headache recurrence). Preventive therapy is indicated for all individuals with CM and for those with EM that have high frequency of attacks ([Lipton and Silberstein 2015](#)). If given during CM, prophylactic treatments could revert the patients to EM and continue to provide benefit after remission is achieved ([Manack et al 2011](#)). Most specialists require that a child experience a minimum of 1 headache per week or 3 to 4 headaches per month to justify prophylactic medication. Children who report intensive and prolonged headaches (lasting more than 48 hours), even if infrequent, may also be offered prophylactic therapy ([Kacperski 2015](#)). It is recommended that an adequate trial of at least 6 to 8 weeks should be sustained before abandoning a treatment ([Kacperski 2015](#)).

Detailed information on the test investigational medicinal product (IMP) (fremanezumab), nonclinical pharmacokinetics, toxicology studies, and clinical trials/studies are provided in the Investigator's Brochure (IB).

## **2.1. Purpose of Trial**

Authorized medications for the acute and prophylactic treatment of migraine in children and medications that are being used off-label in children have limited evidence to support their use, require ongoing patient monitoring, or are associated with undesirable or intolerable adverse effects (Barnes 2015, Kacperski 2015). Therefore, there is an unmet medical need for a safe and effective prophylactic treatment for EM and CM in the pediatric population.

The purpose of the trial is to determine whether the test IMP is safe and effective in the preventive treatment of migraine in pediatric participants with CM.

## **2.2. Summary of Benefits and Risks**

### **2.2.1. Known and Potential Benefits and Risks of the Test Investigational Medicinal Product and/or Device**

Known risks that do not impact the risk-benefit profile:

- Injection site induration
- Injection site erythema
- Injection site pruritus
- Injection site rash
- Injection site pain

### **2.2.2. Overall Benefit-Risk Conclusion**

Mild and moderate drug hypersensitivity events were observed infrequently and with similar incidence in placebo and fremanezumab in the clinical development program, but no anaphylaxis or severe hypersensitivity reactions were seen. However, it cannot be excluded that severe events may occur in the future. Additional information regarding benefits and risks to participants may be found in the IB.

In summary, the benefit and risk assessment for fremanezumab is favorable following review of the observed clinical adult data.

### 3. TRIAL OBJECTIVES, ENDPOINTS, AND ESTIMANDS

#### 3.1. Primary and Secondary Trial Objectives and Endpoints

The primary and secondary trial objectives and endpoints are as follows:

Objectives	Endpoints
The primary objective of the trial is to evaluate the efficacy of test investigational medicinal product (IMP) as compared to placebo IMP for the preventive treatment of chronic migraine (CM).	The primary efficacy endpoint is the mean change from baseline (28-day baseline period) in the monthly average number of migraine days during the 12-week period after the first dose of IMP.
A secondary objective is to evaluate the safety and tolerability of test IMP in the preventive treatment of CM.	
The safety and tolerability endpoints are as follows:
 
 
• occurrence of adverse events throughout the trial, including local injection site reaction/pain
 
• abnormal standard 12-lead electrocardiogram (ECG) findings
 
• changes from baseline in vital signs (systolic and diastolic blood pressure, pulse, temperature, and respiratory rate), height, and weight measurements
 
• changes from baseline in clinical laboratory (serum chemistry, hematology, coagulation, and urinalysis) test results
 
• abnormal physical examination findings
 
• suicidal ideation and behavior as suggested by the Columbia-Suicide Severity Rating Scale (C-SSRS)
 

A secondary objective of the trial is to further demonstrate the efficacy of test IMP as compared to placebo IMP for the preventive treatment of CM.	
The secondary efficacy endpoints are as follows:
 
 
• mean change from baseline (28-day baseline period) in monthly average number of headache days of at least moderate severity during the 12-week period after the first dose of IMP
 
• proportion of participants reaching at least 50% reduction in the monthly average number of migraine days during the 12-week period after the first dose of IMP
 
• mean change from baseline (28-day baseline period) in the monthly average number of days of use of any acute headache medications during the 12-week period after the first dose of IMP
 
• mean change from baseline (day 1) in migraine-related disability score, as measured by the Pediatric Migraine Disability Assessment (PedMIDAS) questionnaire, at 12 weeks after administration of the first dose of IMP
 
• mean change from baseline (day 1) in quality of life, as measured by the Pediatric Quality of Life Inventory (PedsQL), at 12 weeks after administration of the first dose of IMP
 

Objectives	Endpoints
A secondary objective of the trial is to evaluate the immunogenicity of test IMP and the impact of antidiug antibodies (ADAs) on clinical outcomes in participants exposed to test IMP.	
 
proportion of participants developing ADAs throughout the trial. The impact of ADAs on safety and efficacy will be analyzed if the number of ADA-positive participants allows.
 

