### **8.3.5. Suicidal Ideation and Behavior Risk Monitoring**

The C-SSRS, combined with the Investigator's clinical evaluation, will be used to assess whether the participant has suicidal ideation or behavior and its severity ([Posner et al 2011](#)). The C-SSRS will be completed by a qualified rater trained to administer the scale at the investigational center based on discussion with the participant /caregiver at the time points described in [Table 1](#). Any participant who demonstrates suicidal ideation and/or any suicidal behavior at any point during the trial should be withdrawn from the trial and discontinued from trial treatment. In addition, if a participant endorses suicidal ideation or behavior at any point during the trial (including during screening), the Investigator must explain to the participant /caregiver the need for follow-up with a mental health professional and make any necessary referrals.

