### **9.4. Analysis of Exploratory Objective(s)**

### **9.5. Safety Analyses**

Safety analyses will be performed on the safety analysis set (Section 9.1.1).

Safety assessments and time points are provided in [Table 1](#).

All adverse events will be coded using the Medical Dictionary for Regulatory Activities. Each participant will be counted only once in each preferred term or system organ class category for the analyses of safety. Summaries will be presented for all adverse events (overall and by severity), adverse events determined by the Investigator to be related to test IMP (and/or PFS) (ie, reasonable possibility) (defined as related or with missing relationship) (overall and by severity), serious adverse events, serious adverse device effects, protocol-defined adverse events of special interest, adverse events, and adverse device effects causing withdrawal from the trial. Summaries will be presented by treatment group and for all participants. Participant listings of serious adverse events, serious adverse device effects, adverse events, and adverse device effects leading to withdrawal will be presented.

Changes in laboratory, ECG, and vital signs measurements data will be summarized descriptively. All values will be compared with predefined criteria to identify potentially clinically significant values or changes, and such values will be listed.

Suicidal ideation and behavior will be measured using the C-SSRS. Data for participants with positive findings will be listed.

The use of concomitant medications will be summarized by therapeutic class using descriptive statistics. Concomitant medications will include all medications taken while the participant is treated with IMP.

For continuous variables, descriptive statistics (n, mean, SD, median, minimum, and maximum) will be provided for actual values and changes from baseline to each time point. For categorical variables, participant counts and percentages will be provided. Descriptive summaries of serious adverse events, participant withdrawals due to adverse events, and potentially clinically significant abnormal values (clinical laboratory or vital signs) based on predefined criteria will be provided as well.

If any participant dies during the trial, a listing of deaths will be provided, and all relevant information will be discussed in the participant narrative included in the CSR.

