### 13.9. Trial Procedures and Assessments by Visit

#### 1. Procedures for Screening (Visit 1, Days -28 to -1)

The screening visit (visit 1) will take place not more than 28 (+3) days before the randomization visit (visit 2). The following procedures will be performed at visit 1:

- obtain written informed consent from parent(s) or legal guardian(s) and assent (according to local regulations) from each participant before any trial-related procedures are performed
- inform participants of trial restrictions and compliance requirements
- review medical and psychiatric history
- review headache history
- review lifetime prior medication and treatment history
- review demographic characteristics
- review inclusion and exclusion criteria
- full physical examination (including height, weight, and body mass index)
- triplicate 12-lead ECG
- vital signs measurements
- review adverse events
- review concomitant medications
- clinical laboratory tests

- serum  $\beta$ -HCG and urine pregnancy tests (only female participants who are postmenarchal or  $\geq 12$  years of age); inquire and record start / stop date of menstrual period
- provide electronic headache diary device and instructions
- administer C-SSRS

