8. SAFETY ANALYSIS

8.1. General

The safety population will be used for all safety analyses. Summaries will be presented by treatment group (TEV-48125 225 mg, TEV-48125 120 mg and placebo). TEV-48125 will be presented as actually received unless specified otherwise. A total column will also be provided.

For continuous variables, descriptive statistics (n, mean, SD, median, minimum, and maximum) will be provided for actual values and changes from baseline to each time point. For categorical variables, participant counts and percentages will be provided.

Missing values will be reported as missing and no imputation will be undertaken.

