8.11. Columbia Suicide Severity Rating Scale (C-SSRS)

The C-SSRS, combined with the Investigator's clinical evaluation, will be used to assess whether the participant has suicidal ideation or behavior and its severity (Posner et al 2011). The C-SSRS will be completed by a qualified rater trained to administer the scale at the investigational center based on discussion with the participant/caregiver. Any participant who demonstrates suicidal ideation and/or any suicidal behavior at any point during the trial as per C-SSRS and Investigator's clinical evaluation, should be withdrawn from the trial and discontinued from trial treatment. In addition, if a participant endorses suicidal ideation or behaviour at any point during the trial (including during screening), the Investigator must explain to the participant/caregiver the need for follow-up with a mental health professional and make any necessary referrals. Data for participants with positive findings from the C-SSRS will be listed.

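### Suicidal ideation and behavior on the C-SSRS is a named safety endpoint, but only a listing of positive participants is planned, with no by-arm or post-dose summary

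*Protocol*

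**What the plan says.** Protocol 3.1, the protocol synopsis and SAP 1.1 list "suicidal ideation and behavior as suggested by the Columbia-Suicide Severity Rating Scale (C-SSRS" among the safety and tolerability endpoints, under a secondary objective to evaluate the safety of test IMP. Protocol Table 1 and Section 13.9 schedule the scale at visits 1 to 5.

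The planned output is a listing in both documents. Protocol 9.5: "Data for participants with positive findings will be listed". SAP 8.11: "Data for participants with positive findings from the C-SSRS will be listed". The general rule in SAP 8.1 is "Summaries will be presented by treatment group (TEV-48125 225 mg, TEV-48125 120 mg and placebo", with counts and percentages for categorical variables.

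Three other provisions bear on the point:

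- Protocol 8.3.5, and likewise 7.2, Table 1 footnote q and SAP 8.11, say that a participant with suicidal ideation or behavior at any point "should be withdrawn from the trial and discontinued from trial treatment".
- Footnote q allows for a positive before dosing: "if a patient endorses suicidal ideation or behavior at any point during the trial (including during screening" the investigator has to arrange follow-up.
- Table 1 footnote c fixes ECGs, weight, urine pregnancy tests and blood samples before the injection, then says "All other trial procedures can be performed at any time during the visit". The C-SSRS falls under that last sentence.

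**The concern.** A listing of positives names cases. It does not say how many participants were assessed in each arm, what proportion were positive, or how fremanezumab compares with placebo. Neither document defines a post-dose or treatment-emergent C-SSRS finding, and the listing is not restricted to the period after the first dose.

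This is a placebo-controlled trial in participants aged 6 to 17 with no data monitoring committee, so the final report is where a by-arm result would be expected to appear. If no participant were positive, the listing would be empty and the reassurance would not be quantified. If several were, the reader would have to build the comparison from individual rows, using whatever columns the listing happens to carry.

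**Working it through.** **1. Does another section already create a table?** The planned outputs for the safety endpoints, side by side:

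| Endpoint | Planned output | Where |
|---|---|---|
| Adverse events | Summaries by treatment group, plus listings | SAP 8.4 |
| Laboratory tests | Summaries, shifts, clinically significant values, listings | SAP 8.6 |
| Vital signs | Summaries, clinically significant values, listing | SAP 8.8 |
| ECG | Summaries and shifts from baseline | SAP 8.9 |
| Physical examination | Listed, and abnormal findings summarized | SAP 5.7 |
| C-SSRS | Listing of positives | SAP 8.11, Protocol 9.5 |

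The SAP treats listing and summarizing as separate outputs and states both when it wants both; SAP 9 does so for local tolerability. SAP 8.1 sets how summaries are formatted. SAP 8.11 asks for none, so 8.1 has nothing to format.

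**2. Can post-dose findings be identified?** The scale is given at screening, at visit 2 and at visits 3 to 5. Screening is before the first dose and visits 3 to 5 are after it. Visit 2 may fall on either side of the injection, because footnote c does not fix it. A split by visit number alone would therefore be unsafe.

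**3. Size of arm.** Protocol 9.8 and SAP 2.4 give 133 evaluable per group and 4% discontinuation: 266 / (1 − 0.04) = 277.1, taken to 278, or 139 per arm. The figure reproduces. It is used here only as an approximate denominator, on the assumption that all 139 are dosed and assessed. The true number will be somewhat lower, since SAP 15 removes one site from all analysis sets.

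**4. What n/N would add.** Exact (Clopper-Pearson) two-sided 95% limits for one arm of 139:

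- 0 positives: upper limit 1 − 0.025^(1/139) = 2.6%
- 1 positive: 0.02% to 3.9%
- 3 positives: 0.4% to 6.2%

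The documents give no expected rate. For an assumed true post-dose rate of 1% to 3%, the chance of at least one positive in an arm is 1 − (1 − p)^139, which is 75% at 1% and 99% at 3%.

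**5. An illustrative comparison (assumed counts, not a prediction).** With 6/139 versus 1/139, the proportions are 4.3% and 0.7%, a difference of 3.6 points. The Wilson limits are 2.0% to 9.1% and 0.1% to 4.0%. The Newcombe interval for the difference is:

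- lower: 3.6 − √[(4.3 − 2.0)² + (4.0 − 0.7)²] ≈ −0.4 points
- upper: 3.6 + √[(9.1 − 4.3)² + (0.7 − 0.1)²] ≈ 8.4 points

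(Inputs are shown rounded; the results come from unrounded values.) Even that split has an interval that includes zero.

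**The case against.** The case against has four main parts, and much of it stands.

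*The listing may show what is needed.* Its columns are not specified and could include arm and visit. A reader might infer that the trial will report nothing by arm, or that pre-dose and post-dose positives cannot be told apart. The documents do not support either: they plan no summary, which is a narrower statement. The size of the safety set will also be in the disposition table (SAP 5.2). What that does not give is the number assessed with the C-SSRS after the first dose.

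*The withdrawal rule limits mixing.* Someone positive at screening, or at visit 2 before the injection, should be withdrawn. If never dosed, that person is outside the safety set. If the rule is followed, dosed participants with a pre-dose positive should be few. That stands, so mixing is a secondary reason for the fix.

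*Adverse-event tables cover part of it.* New suicidal ideation or behavior can meet the general definition in Protocol 8.4.1.1, and would then appear by arm under SAP 8.4. It would be wrong to conclude that the plan cannot reveal an imbalance. But the protocol expressly turns clinically significant laboratory, ECG, vital-sign and examination findings into adverse events (8.3.1 to 8.3.4.1) and has no such sentence for the C-SSRS. Withdrawals are summarized by reason, with no suicidality category specified. Neither table is a result for the named endpoint.

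*This is a reporting preference.* Protocol and SAP agree with each other, counts will be small and nothing is powered. True, and it limits the weight of the point. It does not explain why this safety endpoint alone, among those set side by side above, has no planned summary.

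**Conclusion.** The point holds as a cheap improvement. A named safety endpoint, measured at all five visits, has a listing of positives and no planned by-arm count, denominator or post-dose summary. The protocol and SAP do not contradict each other, and the primary analysis is untouched.

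The gain is modest and descriptive: a rate with a denominator and an interval, such as an upper limit of 2.6% for 0/139. That figure assumes about 139 dosed and assessed per arm; the 6-versus-1 split and the 1% to 3% range are assumptions too. The conclusion itself rests only on the wording of the two documents and does not depend on any of these numbers.

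**What to change.** Keep the listing sentence in SAP 8.11 and specify that the listing shows treatment arm, visit and timing relative to the first dose. Add to SAP 8.11, and align Protocol 9.5, one table on the safety analysis set:

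- **Columns:** those of SAP 8.1 (225 mg, 120 mg, placebo) plus pooled fremanezumab.
- **Rows:** n/N assessed (%) with any suicidal ideation after the first dose; the same for any suicidal behavior; and n/N (%) with findings new or worse than the pre-dose C-SSRS.
- **Comparison:** pooled fremanezumab minus placebo, difference in proportions with 95% CI (for example Newcombe), labelled descriptive.
- **Timing rule:** class each visit 2 assessment as pre-dose or post-dose by its actual time relative to the injection. Where that time is not recorded, use the screening assessment as baseline.

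The note to file at the end of the SAP says that the analysis has been conducted. If so, SAP 2.5.2 lets analyses outside the SAP be documented in appendices to the clinical study report, and the table can be added there and labelled as not prespecified.

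The cost is a few sentences and one table from data already collected. The downside is small counts, wide intervals and no powered comparison, so the table should be read as description.
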